1. INTRODUCTION

This protocol tests whether systemic interferon gamma (IFN γ) will increase class I MHC expression in patients with advanced myxoid/round cell liposarcoma (MRCL) and synovial sarcoma (SS). These patients historically have a very poor prognosis with a median survival of less than one year [1]. Our group has been developing T cell therapy for these patients, however a major barrier is the low MHC expression of these tumors. Identification of a systemic agent that up regulates MHC in these tumors is critical for successful development of T cell therapy. IFN γ increases MHC expression *in vitro* in these tumors.

Patient taking part in this study will have had tumor biopsy samples taken before entering the study and tissue will be removed after IFN γ administration to determine whether there has been a change in class I MHC expression. In order to obtain post treatment tumor samples, this trial has been designed to enroll patients with metastatic disease undergoing resection, however, certain patients undergoing resection of primary tumors and patients who have disease easily accessible for a core needle biopsy at bedside may also be eligible.

IFN γ is an FDA approved drug with an established safety profile that has been well studied in cancer patients with multiple studies dating back to the early 1980's. However, it is not currently considered standard of care for any cancer type.

1.1 Introduction to the Prevalence, Biology and Natural History of Synovial Sarcoma and MRCL

Soft-tissue sarcomas cause approximately 3900 deaths annually including a disproportionate number of deaths in children, adolescents and young adults. The median survival for patients with advanced soft tissue sarcoma is 8 to 12 months and only 20 to 25% of patients are alive at 2 years [2].

This protocol is focused on 2 soft tissue sarcoma subtypes: synovial sarcoma (SS) and myxoid/ round cell liposarcoma (MRCL). SS has an incidence close to 800 cases annually and represents about 8% of soft tissue sarcomas. It has peak incidence in the 3^{rd} decade of life [3, 4]. SS is by definition associated with a characteristic t(X;18) translocation resulting in one of the SYT-SSX fusion proteins [5]. Liposarcomas account for approximately 10-20% of soft tissue sarcomas and can be classified into three subtypes each with their own distinct clinical behaviors: pleomorphic, well/de-differentiated and myxoid/ round cell liposarcoma (MRCL). MRCL accounts for 40-50% of liposarcomas and is almost always associated with a chromosomal translocation, most commonly t(12;16)(q13;p11) though a number of less common translocations have also been described [6]. The resultant fusion proteins have an activity that is not well understood [7].

While chemotherapy sensitive sarcoma subtypes including MRCL and SS may respond to first line chemotherapy in a minority of cases (typically Adriamycin and Ifosfamide), in almost all patients, the disease will ultimately progress. Pazopanib is a small molecule tyrosine kinase inhibitor with potent anti-VEGF activity that has been approved for patients with SS and other metastatic soft tissue sarcomas generally (with the exception of liposarcomas such as MRCL). In a phase III clinical trial pazopanib improved progression free survival benefit (PFS) of sarcoma patients by approximately 3 months but

did not demonstrate a statistically significant overall survival benefit (OS). There are no other FDA approved agents for patients with metastatic soft tissue sarcomas [8]. Trabectedin is a drug that has shown promise for liposarcomas and a national phase III trial is currently evaluating its benefit (NCT00210665). However, responses are limited in duration and mortality remains high, suggesting the need for novel approaches [9].

1.2 Expression of NY-ESO-1 in Synovial Sarcoma and MRCL

NY-ESO-1, a member of the family of Cancer Testis Antigens, was first discovered through serological analysis in esophageal cancer patients and was subsequently found to induce a strong cytotoxic T-cell response [10, 11]. As their name implies, CT Antigens, are expressed on a protein level in various malignant tumors and germ cells of the testis but not other adult tissues.

Based on its immunogenicity, NY-ESO-1 is considered to be among the most attractive targets for immunotherapy. It has been targeted in a number of clinical studies including several vaccine trials that have induced serologic, CD4+ and CD8+ T cell responses. Delayed type hypersensitivity responses following NY-ESO-1 vaccination have been associated with long-term survival [12, 13]. Objective clinical responses have been

[figure not shown]

Figure 1: Response to NY-ESO-1 specific T cells. Patient responded in several lung tumor including large RUL tumor (A and B) however a soft tissue tumor progressed in spite of therapy (C and D). NY-ESO-1 was retained (E and F). Class I MHC expression was absent before and after treatment (G and H). observed in melanoma patients following vaccination against NY-ESO-1, including one complete response [14]. T cell therapies targeting NY-ESO-1 have induced both partial and complete responses [15, 16].

A vast majority of synovial sarcomas have been described as expressing NY-ESO-1. In an analysis from Jungbluth et al., 20 of 25 (80%) synovial sarcoma tumors were found to express NY-ESO-1 by IHC. Four of the five tumors not expressing NY-ESO-1 had the biphasic synovial sarcoma subtype suggesting an even higher proportion of NY-ESO-1 expression among the monophasic subtype. Eight of the 20 NY-ESO-1 expressing tumors had homogenous expression [17]. More recently, we have found that MRCL also has a strong prevalence of NY-ESO-1 expression [18]. We tested 25 MRCL tumors and found that all expressed NY-ESO-1 (100%) and that expression was homogenous over 70% of cases. [16].

1.3

1.4 MHC expression in sarcoma tumors

We have found that MRCL tumors have decreased expression of both Class I and Class II MHC molecules. Over 50% of tested patients (13/25) had MHC class I expression that was either undetectable or only focally positive (see Appendix A). Another 36% has MHC class I expression that was only "1+" positive meaning that it was in less than 25% of cells examined. None of the tumors examined had over 50% of cells express MHC class I. MHC II data is similarly decreased. We have also looked for MHC expression in SS tumors. On a tissue microarray stained for class I MHC including 12 SS, seven tumors tested had absent MHC and the other 5 had very weak or focal class I MHC expression. Each of the 4 SS patients who have enrolled on our T cell therapy trial have had their tumors tested for class I MHC and all have been negative.

1.5 Increasing MHC expression in SS and MRCL cell lines using low dose IFNγ

We have now tested 2 MRCL cell lines and 3 SS cell lines with IFN γ *in vitro* and seen up-regulation of class I MHC in each cell line tested. In all but one of the cell lines, marked increases in class II MHC were also observed. One of the SS cell lines, established in our lab from a potential T cell therapy patient, expressed the HLA type A0201. We were able to increase NY-ESO-1 specific killing by treating this cell line with IFN γ at a physiologic concentration 100 U/mL (Figure 2) readily achievable *in vivo* [19, 20].

[figure not shown]

Figure 2: Class I MHC in an A0201+ cell line established in our lab increases from baseline (red) following treatment with IFN γ 100 U/mL (blue). Expression is further increased at the 1000U/mL concentration (green) although this concentration in probably supra physiologic. NY-ESO-1 specific T cell killing is also increased following treatment at the 100U/mL concentration (B). Gp100 (not expressed by this cell line) specific T cells are used as a control for nonantigen specific tumor lysis.

1.6 Increased MHC expression in melanoma tumors using low dose IFNy

A number of agents have been observed to increase MHC expression in vitro in tumor cell lines. For example, both IFN alpha and gamma have both been shown to increase MHC class I and class II molecules *in vitro* in multiple cancer types in numerous studies [21]. We have also seen increased MHC expression in SS and MRCL cell lines following IFN alpha. However, we are not aware of any clinical data demonstrating that systemic administration of IFN alpha increases either class I and II MHC molecules for patients receiving typical doses.

By contrast, IFN γ has been shown to up regulate MHC molecules at low doses $(0.1 \text{mg/m}^2 \text{ once weekly})$ [22] in as little as 1 week in melanoma tumors. MHC evaluation was based on the presence of positive cells in fine needle aspirates of accessible lesions. Two patients in this study had negative MHC class I expression in their tumor and both developed MHC I expression following therapy. For one patient, class I expression was induced after only 1 week of therapy however for the other patient it took 3 months. In 6 of 14 patients starting without class II expression, MHC class II was induced. To be sure, melanoma and soft tissue sarcoma have different biologies and interact with the immune system in markedly different ways thus the need to test for this effect in SS and MRCL patients specifically.

1.7 Toxicities of IFNy treatment

IFN γ has been used extensively in clinical trials for patients with melanoma both in the metastatic as well as adjuvant settings. Currently it is FDA approved for patients with chronic granulomatous disease as well as a treatment for severe osteoporosis. Response rates for patients with metastatic melanoma treated with IFN gamma have ranged from 5-15% with including a handful of complete responders [22, 23]. IFN γ has been found to be safe and relatively well tolerated even at doses significantly higher than we are proposing to use in this study.

A large phase I study treated 98 patients with metastatic melanoma at doses up to 0.9 mg/m^2 administered IV (rather than subcutaneously) three times per week for at least 8 weeks. This study had no fatalities but did see several cases of grade 4 toxicities including anemia, myalgias, renal (proteinuria) and heaptic toxicity at higher doses. There were also 3 cardiac events that occured in patients on that trial.

A phase III randomized trial was run by SWOG in the early 1990's designed to test the benefit of IFN γ in the adjuvant setting [24]. This trial included 133 patients who completed 1 year of daily IFN gamma and were evaluated for toxicity. There were no fatal complication or grade 4 toxicities, however, 24 patients had grade 3 toxicities including 4 patients with grade 3 myelosuppression, 3 patients with grade 3 neurologic toxicities (confusion, insomnia, personality change) as well as other toxicities including depression, migrane, transaminitis, pruritus, and flu like symptoms. The most common toxicities were fever/chills and headache. It is unclear at what point of the year of therapy patients developed the grade 3 toxicities. Dosing in this trial gave each patient 0.2 mg of IFN γ subcutaneously daily, similar to the 0.1mg/m² considered to be low dose. Although the

authors of the study concluded that single agent IFN gamma had no clinical benefit for melanoma patients in the adjuvant setting, it was safe and generally well tolerated.

The low doses of IFN γ proposed in this study (0.1mg/m² weekly) were examined in 19 patients who received up to six months of therapy. No patients on this study had grade 3 or grade 4 toxicity. The most common toxicity were flu-like symptoms (grade 1). Grade 2 toxicities included fever (2 patients) as well as chills, myalgias, flu-like symptoms and leukopenia (1 patient each). IFN γ has also been used in prior trials safely in the perioperative period both right before surgery [25] and after surgery [26].

1.9 Surgery in patients with metastatic sarcoma

In order to test whether IFN γ increases class I MHC expression, we have chosen to include patients in a number of different clinical scenarios. Primary tumors where there is a recent biopsy specimen available can participate (so long as the patient has not received systemic therapy or radiation since the biopsy was performed). Patients with metastatic disease who have a painful untreated primary tumor they would like remove may participate. Patients with lesions accessible to bed side core needle biopsy will be allowed

to participate. However, our expectation is that one of the most common situations for patients considering this trial are patients with oligometastatic lung metastasis considering resection.

[figure not shown]
When metastatic disease is operable, removal is frequently considered the optimal choice. While a randomized control trial comparing a surgical approach to a non-surgical approach would be impossible, retrospective analysis and historical controls seem to suggest a benefit. For example, in a large analysis performed by the MSKCC [27], overall survival of sarcoma patients undergoing resection for metastatic disease was significantly increased relative to a similar historical group of patients (15 vs. 11 months). Isolated cases of patients with long-term disease free survival following metastetectomy have been reported [28]. In patients where complete resection can be achieved, survival at 3 years has been reported above 30%, particularly when the burden of disease is low [29]. Patients with a significant disease free interval or who relapse with only a small volume of disease after an initial metastatectomy may benefit from a second surgery [30]. Radiotherapy is another option for patients with a few isolated sarcoma metastasis [31].

Despite the potential benefits of surgery for some patients with metastatic sarcoma, there are patients who will not benefit. Some patients will rapidly progress despite surgery and undergo a major operation without any clinical benefit from it. Standard practice is to wait and observe the patient either with or without systemic therapy in order to assess the pace of disease before bringing the patient to surgery in order to avoid performing an

unnecessary procedure on a patient with rapidly progressing disease [32-34]. It is during this waiting period that we expect to treat the majority of patients on this study.

1.10 Results of the study to date

To date we treated six patients; all evaluable biopsy specimens showed dramatically increased MHC expression; by flow cytometry, HLA-ABC expression rose from a mean of 3.3% to 17.0% (Fig. 2A and B). Markedly increased CD3+ cell infiltration was also observed (Fig. 2B). In order to interrogate the specificity of these T cells, TIL were expanded from each 1-2 mm core samples and using an ELIspot assay consisting of overlapping 15 amino acid peptides (Fig. 2C) from the most immunogenic regions of cancer testis antigens (including NY-ESO-1), we found that post-treatment T cells had improved recognition of these antigens. Thus, a single inflammatory cytokine can dramatically alter each component of the TME state. We are very pleased that based on our results a Cancer Immunotherapy Trials Network Study is being planned combining IFNy with pembrolizumab. However, even though we believe that the study has met its primary end point and demonstrated increased MHC expression following IFNy treatment in these sarcoma tumors, we are seeking to treat up to four additional patients in order to have better data regarding our secondary objectives, specifically to study the

PD-L1+ macrophages, which we have observed increased in the tumors of three of the patients treated on the study to date.

2. OBJECTIVES

2.1 **Primary Objectives**

• To determine whether systemic administration of IFNγ will increase class I MHC expression in SS and MRCL tumors.

2.2 Secondary Objective

- To determine whether systemic administration of IFNγ will increase class II MHC expression in SS and MRCL tumors.
- To examine changes in the immune response to MRCL and SS by examining changes in the immune infiltrates, antibody response and antigen specific T cell response before and after IFNy treatment.

3. STUDY DESIGN

This protocol will test whether systemic IFN γ will increase class I MHC expression in patients with advanced myxoid/round cell liposarcoma (MRCL) and synovial sarcoma (SS).

Patients with available prior tissue may use this as their pre-treatment sample. Patients may also have a research biopsy prior to receiving IFN γ . For their post IFN γ sample, patients may either have surgery or biopsy as part of their standard care or have a research biopsy.

Ten patients will receive 4 weeks of low dose weekly IFN γ at a dose of 100 mcg/m². If there are any issues regarding data from any of these patients, additional patients may be enrolled as replacements as the discretion of the PI. Patients will be given a patient log marked with the scheduled dates for IFN γ administration. They will be instructed to record the day and time of IFN γ administration in their logs.Deviations of up to 48 hours in administration of IFN γ will be permitted while on the weekly schedule and up to 24 hours while on the three times weekly schedule. The final tumor sample should be taken 24-48 hours after the last dose of IFN γ and not more than 72 hours.

While not ideal, the length of time that a patient is on IFN γ with either regimen could be extended to up to 8 weeks to accommodate the scheduling changes sometimes necessary in the course of patient care. The patient may also stop IFN γ and restart to accommodate a scheduling delay. Any such change in IFN γ must be approved by the PI.

If there is a patient who would be a good study candidate except that surgery is scheduled (or is being scheduled) too soon for them to receive 4 weekly doses of IFN γ , but they could receive at least 2 doses of IFN γ , they may participate and receive only 2 doses.

While response to IFN γ is not an endpoint of the study and no imaging is planned to evaluate response, should a clinical response to IFN γ be noted through the normal course of clinical care, it is conceivable that a situation would develop where it was determined that continuation of IFN γ will clinically benefit the patient (e.g. if the patient's tumor appears to be responding). In this case, IFN γ may be continued at the discretion of the PI and the treating physician.

For research biopsies, ideally 4-6 cores will be collected. Unless otherwise specified by the PI, one will be placed in formalin for IHC. The other samples should be placed in

RPMI for analysis by the [name] Lab. Biopsies may be done in the clinic at the SCCA if deemed safe and appropriate by the treating clinician. Alternatively, biopsies may be done under ultrasound guided at the University of Washington.

Data from the study including patient outcomes and biomarker related information learned from analysis of patient samples may be shared with Horizon Pharma who will now be providing drug for the study.

4. **PATIENT ELIGIBILITY**

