4.1 Inclusion Criteria

- 4.1.1 A diagnosis of synovial sarcoma and myxoid/ round cell liposarcoma
- 4.1.2 Male or female subject, 18 or older
- **4.1.3** A superficial tumor easily and safely accessible for a research biopsy or are being considered for resection or biopsy of their tumor as part of standard of care and have recent pathology.
- **4.1.4** Zubrod performance status of '0-2' or Karnofsky score >60%. (Appendix A)
- **4.1.5** No treatment with systemic anti-cancer treatment (chemotherapy or biologics) within 2 weeks of starting interferon gamma.
- **4.1.6** Patients with a history of coronary artery disease must have had a normal stress test within 180 days of starting IFNγ.
- **4.1.7**. Must have been off metformin for at least 2 weeks prior to starting IFNγ.
- **4.1.8** No use of full dose, therapeutic anti-coagulation. However, low dose warfarin for catheter prophylaxis or acetylsalicylic acid are acceptable.
- **4.1.9** No thrombotic event within 6 months (deep vein thrombosis, pulmonary embolism) of starting IFNγ.

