4.2 Exclusion Criteria

- 4.2.1 Active infection requiring oral or intravenous antibiotics
- **4.2.2** Pregnant women, nursing mothers, men or women of reproductive ability who are unwilling to use effective contraception or abstinence. Women of childbearing potential must have a negative pregnancy test within two weeks prior to entry.
- **4.2.3** Serum creatinine > 1.5 mg/dL or Glomerular Filtration Rate <50.
- **4.2.4** Significant hepatic dysfunction (SGOT > 150 IU or > 3x upper limit of normal; bilirubin > 1.6 mg/dL; prothrombin time > 1.5 x control).
- **4.2.5** Known CNS metastasis. Once CNS metastasis have been treated these patients may participate if they are otherwise good trial candidates.
- **4.2.6** Current treatment with steroids (must be discontinued 1 week before starting IFN γ).
- **4.2.7** Hemoglobin A1C >8.5%.
- **4.2.8** Uncontrolled hypertension, BP >150/100mmHg. Patients with elevated BP may enroll once BP is corrected.
- **4.2.9** NY-ESO-1 specific T cell therapy within 1 year of starting on the trial.
- **4.2.10** New (<6 months) cardiac arrhythmia (EKG should be performed within 2 weeks of starting IFN γ .
- **4.2.11** History of clinically significant congestive heart failure.

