6. INVESTIGATIONAL PLAN

All patients will have available tissue prior to study entry. The first two patients will receive low dose IFN γ (0.1mg/m²) by sub-cutaneous administration at a dose of 0.1mg/m² for four weeks prior to surgery. Injection should be given every 7 days though an allowance of 2 days before or after will be acceptable to accommodate specific circumstance. Any deviation from the recommended schedule of IFN γ dosing must be discussed with the PI. Patients or their caregiver will be instructed on subcutaneous self-administration. The last

dose of IFN γ will be given 24-48 hours prior to surgery (absolutely not more than 72 hours).

10 patients will be treated on this regimen.

Paraffin embedded tissue will be tested for class I MHC, class II MHC and NY-ESO-1. Immune infiltrates in tumors will be studied using IHC staining for CD3, CD4, CD8, CD57, CD68 and FoxP3. Antibody responses will be examined by [name] (Tisch Cancer Center). In patients with the HLA types A0201 and A2402 antigen specific T cell responses to NY-ESO-1 will be examined using MHC tetramers in the peripheral blood. In patients with the HLA type A0201, PRAME, MAGE family and CAMEL specific T cell responses will also be examined using MHC tetramers. In patients will large tumors that are resected, immune infiltrates will be examined directly by flow cytometry for markers of T cell memory (CD45RO, CD27, CD28, CCR7, CD62L, CD127) and when possible look for tumor infiltrating antigen specific T cells using MHC tetramers. When enough tumor is available RNA will also be extracted for possible future analysis.

Toxicity will be recorded and graded according to the NCI CTCAE v 4.0 at each visit.

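### For prior-tissue baselines other than primary tumors, therapy given between the baseline sample and IFN gamma is neither ruled out nor reported

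*Combined protocol and SAP*

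**What the plan says.** The protocol expects tissue to exist before enrollment. The Introduction says that patients "will have had tumor biopsy samples taken before entering the study", and Section 6 says: "All patients will have available tissue prior to study entry". Section 3 then allows that tissue to be the baseline: "Patients with available prior tissue may use this as their pre-treatment sample". A research biopsy before IFN gamma is offered there as an option, not required.

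Section 1.9 attaches a condition to primary tumors with a recent biopsy. They may take part "so long as the patient has not received systemic therapy or radiation since the biopsy was performed". The sentences that follow, on painful primaries in metastatic disease, on lesions within reach of a bedside core biopsy and on lung metastases, do not carry it. Section 4 does not restate it. Yet Section 1.9 expects that "one of the most common situations for patients considering this trial are patients with oligometastatic lung metastasis considering resection".

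Four other rules bear on the point:

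- 4.1.3 admits patients with an accessible superficial tumor, or those who "are being considered for resection or biopsy of their tumor as part of standard of care and have recent pathology".
- 4.1.5 requires: "No treatment with systemic anti-cancer treatment (chemotherapy or biologics) within 2 weeks of starting interferon gamma".
- 4.2.9 excludes "NY-ESO-1 specific T cell therapy within 1 year of starting on the trial".
- 7.2 forbids other anti-cancer treatment during the study, and commits to reporting steroid use in every analysis.

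**The concern.** The primary objective (class I MHC) and the immune-infiltrate objective are both answered by a change within the patient, with no control arm. The contrast is clean only if IFN gamma is the one treatment given between the two samples. The authors apply this reasoning to primary tumors but not to the metastatic patients whom they expect to be common.

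Section 1.9 makes the gap plausible. It describes a period of observation before metastasectomy that may include systemic treatment, says most patients are expected to be treated on study during that period, and names radiotherapy as an option for isolated metastases. If such treatment followed the baseline sample, its effect on MHC or infiltrates would be inseparable from that of IFN gamma. A reader could not tell which patients this concerns unless the baseline date and intervening therapy were reported.

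**Working it through.** **The plan's own figure.** Section 10 gives over 90% power for four patients, an effect size above 2.5 and two-tailed alpha 0.05. Taking the effect as a standardized paired change (an assumption), a paired t-test has 3 degrees of freedom and noncentrality 2.5 × √4 = 5. Power is 0.899 at 2.5 and 0.917 at 2.6, so the figure reproduces. This point does not depend on it.

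**Is the gap open?** Take a hypothetical patient with a lung metastasis. Prior tissue is the baseline. Chemotherapy starts after that sample and ends 15 days before the first IFN gamma dose, and a metastasis is irradiated before enrollment.

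| Rule | What it covers | Does it stop this case? |
|---|---|---|
| 1.9 condition | Primary tumors | No, the lesion is a metastasis |
| 4.1.3 | Recent pathology, undefined; silent on treatment | Not clearly |
| 4.1.5 | Systemic drugs, 14 days back from first dose | No, 15 > 14, and radiation is not named |
| 4.2.9 | One T cell therapy | No |
| 7.2 | Therapy while on study; reporting of steroids | No |

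No item in 4.1 or 4.2 addresses earlier radiation, and none counts time from the baseline sample. The case is permitted, and no available text requires it to be reported.

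**How far is the later sample from the last systemic drug?** At least 14 days pass before dose 1. Four weekly doses add 3 × 7 = 21 days, and the final sample follows 1 to 2 days later: 14 + 21 + 1 = 36 to 37 days. With the two-dose exception it is 14 + 7 + 1 = 22 to 23 days. Permitted dose deviations shift these slightly.

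**What would setting flagged patients aside cost?** These figures measure lost sample size, not bias. The plan specifies no sign test; it is used here only as a yardstick. With n patients all rising, the exact two-sided p is 2 × 0.5ⁿ, and the lower 95% limit for the proportion rising is 0.025^(1/n).

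| n | p | Lower limit |
|---|---|---|
| 9 | 0.004 | 66% |
| 8 | 0.008 | 63% |
| 7 | 0.016 | 59% |
| 6 | 0.031 | 54% |
| 5 | 0.06 | 48% |
| 4 | 0.13 | 40% |

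Section 10 reports five evaluable patients, all with an increase, so n = 5 is the position to date and each patient is 1/5 = 20% of it. The rows for n = 6 to 9 are hypothetical: n = 9 assumes that all four added patients are evaluable and rise (5 + 4), and each row below it sets one more flagged patient aside.

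The 95% half-width for a mean paired change, in SDs of the change, is t(0.975, n − 1)/√n. It is 0.77 at n = 9 and 0.84 at n = 8. For the four added patients alone it is 1.59, and 2.48 if one is set aside.

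**The case against.** The strongest reply is that exposure is limited.

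- Section 1.10 reports flow cytometry and T cells expanded from small cores. Such assays point to fresh tissue rather than stored blocks. This stands as a reason to expect that some baselines were fresh, but does not show that all were.
- Superficial or bedside-accessible lesions can supply a fresh baseline. This stands, and it leaves mainly lung metastasectomy patients using prior tissue. But the fresh biopsy is optional.
- The washout and dosing period put about 5 weeks between the last systemic drug and the final sample, so a rival effect would have to persist that long. This narrows the concern for drugs, less so under the two-dose exception (about 3 weeks), and does not address radiation.
- The pre-treatment history and the checks behind 4.1.5 and 4.2.9 probably capture much of the treatment information. This stands in part. What is missing is a commitment to tie it to the baseline date and report it.
- In Figure 1, one progressing lesion lacked class I MHC both before and after T cell therapy. That argues against an upward bias, but weakly: it is one lesion, and a therapy that 4.2.9 restricts.

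A reader might infer that the increases seen so far are confounded. The documents do not support that. They show what is permitted, not that it happened. Nor do they support saying that every patient's baseline is unprotected, since primary tumors are covered in Section 1.9.

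**Conclusion.** The point holds in a limited form. For prior-tissue baselines other than primary tumors, the plan allows systemic therapy that ended more than 2 weeks before IFN gamma, and any pre-study radiation, to fall between the two samples, and no available text asks for it to be reported. A change in such a patient could not be attributed to IFN gamma alone.

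The number of patients affected and the size and direction of any bias cannot be determined. The sample is small enough for a single case to matter: one of five evaluable patients to date, or one of the four added for the macrophage question. In the hypothetical nine-of-nine case, the sign-test yardstick stays below 0.05 with up to three patients set aside. That shows how much sample could be lost; it does not bound the bias. The reading assumes that the protocol text not available here contains no further rule. The point warrants a change to the plan but does not undermine the reported findings.

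**What to change.** 1. Keep the Section 1.9 condition as a participation rule for primary tumors using prior tissue, and state it in Section 4. It should not be relaxed.
2. For every other prior-tissue baseline, if systemic therapy or radiation was given since the sample, prefer the research biopsy that Section 3 already allows where the lesion is accessible. Otherwise enroll the patient and flag the baseline.
3. For all ten patients, record the baseline sample date, the lesion sampled before and after, and any systemic therapy or radiation between the baseline sample and the first dose, noting whether radiation was to a sampled lesion.
4. Report this in all analyses, as 7.2 does for steroids. Show class I MHC and immune-infiltrate results with and without flagged patients.

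The cost is a short addition to Section 4, a few case report form items and a chart review for the six patients already treated. No biopsy becomes mandatory, and no patient who is now eligible is turned away. The analysis without flagged patients is less precise, and for the four added patients alone it can only be descriptive. Section 3 lets the PI enroll replacements, which could offset the loss.
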